#### G. Risks and Side Effects:

1. Describe any potential risks--physical, psychological, social, legal, or other and assess their likelihood and seriousness. Describe the alternative treatments and procedures that might be advantageous to the subjects.

The potential risks of this study are mainly those associated with the B & O suppositories: Belladonna may cause drowsiness, dry mouth, urinary retention, photophobia, rapid pulse, dizziness and blurred vision. Opium usage may result in constipation, nausea or vomiting. Pruritis and urticaria may occasionally occur. These risks are relatively mild as far as medication side effects go. Alternative treatments or procedures for patients undergoing lithotripsy who may experience bladder spasms include the option of treating bladder spasms with narcotic pain medications, oxybutynin, an oral antimuscarinic, or not treating the patient at all. Any of these choices carry side effects or negative consequences. Not all patients who undergo lithotripsy procedures will experience bladder spasms post-operatively, but those that do will be exposed to possible side effects with treatment. Side effects of oxybutynin are included on the package insert attached to this form.

2. Describe the procedures for protecting against or minimizing any potential risks, including risks to confidentiality, and assess their likely effectiveness. Discuss provisions for ensuring necessary medical or professional intervention in the event of adverse effects to the subjects. Describe the provisions for monitoring the data to insure the safety of subjects.

Risk will be minimized by strictly adhering to the exclusion protocol to ensure that patients at an increased risk for adverse effects are not exposed to the suppositories.

To reduce the risks to confidentiality, all data will be recorded in electronic format, kept on a computer meeting the GW university standards for antivirus software, and will require password entry for access to the computer itself as well as the document in which the data is stored. Data transferred from the electronic medical record system to the computer database will be de-identified and given a new unique identifier. The key document to justify the new unique identifier with the subject MRN and DOB identifying information will be stored on a separate computer with the same protections in place as described above. This key will be deleted at the conclusion of the study. If at any time during the study any materials or the computers with the electronic documents pertaining to the study are found to be missing or otherwise compromised, the GW OHR will be immediately notified.

Patient's will be monitored in the post-operative setting, and any adverse effects will be treated as part of the normal post-operative course of care.

3. Discuss why the risks to subjects are reasonable in relation to the anticipated benefits to subjects and in relation to the importance of the knowledge that may be reasonably expected to result.

The risk to subjects are very minor side effects, while the benefit is that they could gain relief from the severe discomfort of bladder spasms in the post-operative setting. The importance of this knowledge is in trying to find a better, more efficient way to prophylactically treat bladder spasms.

4. List all risks that are more than minimal (no greater probability or magnitude than those ordinarily encountered in daily life or during routine medical tests). Include physical, psychological, social, economic, legal or other risks, where present.

The physical risks that are more than minimal include those side effects listed above. Psychological risk should be minimal. Social risk will be none. Economic risk, patient's only are exposing themselves to a slightly added cost. Legal risk should be none.

5. Describe the severity and probability of all material risks, and the implications, in understandable terms. Use a table for Common (21-100/100), Occasional (5-20/100) and Rare (<5/100) risks sorted by Immediate (1-2 days of treatment), Prompt (within 2-3 weeks before next course), Delayed (any later time during treatment) and Late (after completion of treatment) onset wherever possible.

All risks are considered immediate (1-2 days of treatment).

Common: constipation, dry mouth

Occasional: difficulty urinating

Rare: blurred vision, dizziness, nausea, vomiting, sensitivity to light

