Here, we will want to detect a 20% difference between groups. Assuming that in the treatment group, 20% of patients need rescue medication for bladder spasm, while 40% need such meds in the control group, we would need n=82 per group (total N=164) in order to detect a difference this large with power >.80.

Therefore, in order to have adequate power across all 3 outcome measures, we plan to enroll a total of 180 subjects, randomized equally across treatment and control groups.

6. Identify all drugs and devices to be used, if applicable,. If the drug or device is investigational under FDA policy, list the actual IND/IDE number and respective source, supplier, and/or sponsor. If an IND/IDE has been assigned provide the FDA

stage status. Note the proposed dosage related information including instructions for administering, adverse effects, compatibility in infusions, and stability.

Please see package inserts for B and O suprette suppositories attached to this submission. We are also including Ditropan, which is the oral anti-muscarinic to be included in this study. The dosage of B&O will be 16.2mg/30mg which is in the formulary at GW. Ditropan will be given in the normal 5 mg dosage.

7. Identify all procedures that will be used for the purpose of this research. If blood is to be drawn, indicate amount to be withdrawn per single withdrawal, and the total amount of blood to be drawn. If transfusions are anticipated, include assurance that the volume of blood removed for research purposes will not necessitate a transfusion. [Refer to Section 1.5.5]

E. Study Population –(Gender and Minority Inclusions):

1. Describe the characteristics of the subject population, include the anticipated number of normal volunteers, age ranges, sex, ethnic background, and health status.

Identify the criteria for inclusion or exclusion (especially women and/or minorities).

Explain the rationale for the use of special classes of subjects, such as fetuses, pregnant women, or others who are likely to be vulnerable, especially those whose ability to give voluntary informed consent may be questionable.

The subject population will be patients seen at GW for lithotripsy procedures. This will include men and women ages 18-89. It will include all ethnic backgrounds, and anyone who has been cleared for surgery.

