The criteria for exclusion for those patients who agree to participate in the study will be patients with glaucoma, severe hepatic or renal disease, bronchial asthma, respiratory depression at the time of administration, convulsive disorders, allergy to anti-muscarinics or opiates, history of anorectal surgery, pre-operative use of antimuscarinics, chronic pain, chronic use of analgesics, or a history of alcohol or opioid dependency, pregnant women and nursing mothers.

F. Human Subjects (Risks & Benefits)

1. Identify sources of research material obtained from individually identifiable living human subjects in the form of specimens, records or data. Indicate whether the material or data will be obtained specifically for research purposes or whether use will be made of existing specimens, records or data. Subjects with specific diseases or conditions are often identified as potential subjects through some type of record

(e.g., medical records, patient charts, registries for cancer cases, surgical or X-ray log books, school records). Controls may come from the same population as the subjects (which is always the case in a randomized clinical trial), be persons with unrelated conditions or be volunteers from the general population.

No material from individual human subjects will be used. All information obtained will be through patient surveys and the patient's medical records.

2. Describe plans for recruitment of subjects and the consent procedures to be followed; including the circumstances under which consent will be sought and obtained, who will seek it, who will give consent, the age range of the individual who will give consent, the nature of the information to be provided to prospective subjects, payment for participation (if applicable), the prospective subjects, and the method of documenting consent. (State if you are requesting a 'waiver of consent' from the IRB and why.) [Refer to Section 3.0]

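### The exclusion list is the stated safeguard against exposing higher-risk patients, yet it has no item for known urinary retention, a belladonna risk the plan itself names

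*Combined protocol and SAP*

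**What the plan says.** Section G.1 gives the drug's expected effects: "Belladonna may cause drowsiness, dry mouth, urinary retention, photophobia, rapid pulse, dizziness and blurred vision". The instruction in G.5 asks for risks to be sorted by frequency, including "Occasional (5-20/100) and Rare (<5/100) risks", and the plan's answer contains the entry "Occasional: difficulty urinating".

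Section G.2 says how risk will be kept down. Its measure before exposure is strict use of the exclusion criteria, "to ensure that patients at an increased risk for adverse effects are not exposed to the suppositories". The same answer later adds that patients are monitored after the operation and that adverse effects are treated within usual care.

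The exclusions appear once, in Section E.1. The list opens with "patients with glaucoma, severe hepatic or renal disease, bronchial asthma, respiratory depression at the time of administration, convulsive disorders". Its middle part reads "allergy to anti-muscarinics or opiates, history of anorectal surgery, pre-operative use of antimuscarinics, chronic pain, chronic use of analgesics". The remaining items are past dependency on alcohol or opioids, pregnancy and nursing. Otherwise E.1 admits men and women aged 18 to 89: "It will include all ethnic backgrounds, and anyone who has been cleared for surgery".

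Section D, item 2, assigns both active arms a B and O suppository in the operating room. One arm receives it once anesthetized and before the urologic procedure, the other after the procedure.

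**The concern.** G.2 makes a specific claim for the exclusion list: patients more likely to suffer adverse effects will not be exposed. The list can keep that promise only for conditions it contains. Urinary retention is an effect the plan itself attributes to the drug, and the related complaint is not placed in the lowest frequency class. Yet a patient already known to have retention passes every written criterion.

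What is at stake is the safety of a subgroup whose size is not given. This is not an objection to dosing before spasms appear, which is the study question. It has no bearing on the efficacy comparison, the sample size or the analysis.

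**Working it through.** The plan gives no figure to reproduce, and no arithmetic bears on the point. The check is a reading of the eligibility text against the risk text.

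1. *Is retention a risk named by the plan?* Yes. It is listed in G.1, and the related complaint, difficulty urinating, is rated Occasional (5-20/100) in G.5.

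2. *What stands between a higher-risk patient and the drug?* In G.2, only the exclusions act before exposure. Monitoring and treatment act afterwards.

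3. *Does any exclusion cover known retention?* Taking the list item by item:
   - Glaucoma, bronchial asthma, convulsive disorders, respiratory depression and allergy concern other conditions.
   - Severe hepatic or renal disease is a different condition; a patient can have retention without it.
   - Anorectal surgery concerns the rectal route.
   - Pre-operative antimuscarinic use limits additive drug exposure. It does not remove a patient with retention who takes no such drug.
   - Chronic pain, chronic analgesic use, alcohol or opioid dependency, pregnancy and nursing do not concern retention.

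   No item covers it, and no other section adds one.

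4. *Is such a patient otherwise eligible?* Yes, if cleared for surgery, within the age range and free of the listed conditions.

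5. *Would the patient actually be dosed?* In either active arm, yes. Section D, item 2, states the administration as part of the assignment. The surgeon's discretion over B and O is written there for control patients who develop spasms, not for withholding an assigned dose. Section O describes a written prescription for the suppository but gives no rule for declining to write it.

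6. *Does the timing matter?* G.1 accepts that not every patient will have spasms. Dosing in the operating room comes before that is known, so some active-arm patients receive a drug for which no symptom would have arisen. Active-arm patients who do have spasms are then offered Ditropan, which the plan describes as an oral antimuscarinic.

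Steps 1 to 5 show that, followed exactly as written, the list does not deliver what G.2 claims for it in the case of this one named risk.

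**The case against.** Five arguments can be made for the plan.

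*Specialists control access.* Patients are identified in a urology clinic or among the attending urologists' own patients, must be cleared for surgery, and need a prescription for the suppository. Section I adds a review by the anesthesia department, described as covering anesthetic interactions. This makes an unsuitable dose less likely. It stands as mitigation, but none of it is a written rule on retention, and G.2 rests on the list rather than on judgment.

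*Patients are monitored and treated.* This also stands. It would be wrong to say that the exclusions are the only protection. But monitoring begins after exposure, whereas G.2 promises that exposure will not happen.

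*The dose is accepted practice.* Section D describes B and O as well accepted after urologic procedures, with only the timing changed, and Section G calls the risks mild. That lowers the priority. It does not settle whether a patient who already has retention should be given the drug before any symptom calls for it.

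*A list need not mirror every side effect.* Constipation is rated Common and has no matching exclusion either. True, and a missing match alone would prove little. The point rests on the explicit claim in G.2, together with the inference that known retention marks a patient as higher-risk for this effect.

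*The package inserts may cover it.* They are described as attached but are not available here, so any precaution in them cannot be checked, and their absence is no fault of the plan. The protocol does not say that contraindications in the inserts serve as trial exclusions.

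**Conclusion.** The point holds as a gap in eligibility. The plan names urinary retention as a drug risk, relies on the exclusions to keep higher-risk patients from exposure, and has no exclusion for known retention. It is a cheap safety improvement of low to moderate priority.

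It rests on one assumption: that existing retention raises the risk of the retention effect. This is a clinical inference from the named side effect; the documents do not state it.

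No size can be attached. A reader might apply the 5-20/100 rating to the difference in drug use between active and control patients and read the result as the harm from this gap. The documents do not support that. The calculation would give the same answer for patients without retention, so it measures prophylactic against as-needed dosing. The quantities needed, namely how many eligible patients have known retention and how far it raises their risk, are not given.

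A reader might also infer that bladder outlet obstruction should have been excluded. The documents do not mention that condition, so the point is confined to retention, which they do name.

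**What to change.** Add one line to the exclusions in Section E.1: *current or known urinary retention, as judged by the urologist*. Check it from the history or chart at consent, whether in the clinic, in the emergency room or just before surgery (Section F.2), or when the suppository is prescribed (Section O). The statement in G.2 would then hold for this risk.

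The cost is one eligibility line by amendment and slightly narrower eligibility. No new test or visit is needed, and the planned comparisons and sample-size reasoning are unaffected.

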-2. The patients will be divided into three research arms. Patients will be randomly selected for one of the groups using a random number generator between 1 and 3. There will be a "Control Group" which will receive a rectal exam while still in the operating room in the lithotomy position after the procedure. There will be a "Postoperative OR" group which will receive a B and O suppository while still in the operating room in the lithotomy position after the procedure. Finally, there will be a "Preoperative OR" group which will receive a B and O suppository after the induction of anesthesia prior to beginning the urologic procedure in the lithotomy position. The "Control Group" will receive a rectal exam in the operating room after the procedure but before extubation to simulate the effects of suppository administration so that we know that any effects are due to the medication and not to the placement of the suppository itself. Those patients in the "control group" may receive a B and O suppository as part of standard procedure in the post-operative period if these individuals experience any bladder spasms and wish to have this as a treatment. This administration will be at the discretion of the operating surgeon as it is in standard cases. Patients may also receive Ditropan in the post-operative setting, which is part of the standard procedure for treating bladder spasms following urologic procedures. Patients in the postoperative and preoperative OR groups will be offered Ditropan for any bladder spasms in the post-operative setting to control symptoms, which is part of the normal standard of care for anyone who has already received a B and O suppository with inadequate control of symptoms. All patients will be treated with a normal post-operative pain regimen which may include narcotics. This will be at the discretion of the treating physician.

-3. In the post-operative setting, all subjects will be given a quick survey within 24 hours to assess their amount of discomfort related to bladder spasms/urinary discomfort. In addition, subjects medical charts will be reviewed to determine the amount of antimuscarinics that the patient received 24 hours post-operatively and the amount of narcotic and non-narcotic pain medication that subjects required. Patients not in the experimental arm will be given oral anti-muscarinics to treat any bladder spasms that they may have, but will not be given suppositories.

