-4. Data will be entered into the database following the procedure as available.

-5. Subjects will have clinically appropriate follow-up per the attending urologist. If, as part of that follow-up, clinically relevant events occur, the corresponding data will be recorded in the database.

Note that, with the exception of which particular study arm the subjects are enrolled into and the recording of data as detailed above and below, there will be absolutely

no difference in the care received by patients choosing to participate in this study and those who elect not to participate.

Data will be analyzed using commercially available statistical software. T-tests will be performed for continuous variables and Pearson's Chi-squared tests for categorical variables. Analysis will be tailored to compare B and O Supprenettes Suppositories and placebo/no suppository in order to best answer the research question.

1. Describe any new methodology and its advantage over existing methodologies.

There are no methodologies in this protocol which are new.

2. Discuss potential difficulties and limitations of the proposed procedures and alternative approaches to achieve the aims.

The procedure is designed so that patients receive a B and O suppository as they would as part of standard protocol in the post-operative period if bladder spasms were experienced. The only difference is regarding timing of administration. Therefore, there are no potential difficulties or limitations of the proposed procedure since B and O administration is already a well-accepted treatment for bladder spasms following urologic procedures.

3. Provide a tentative sequence or time table for the study.

November 2015 - IRB approval and begin recruiting patients for study

December 2015 - June 2016 Conducting study according to aforementioned protocol

July 2016 - Begin data analysis and manuscript preparation

4. Specify procedures, situations, or materials that may be hazardous to personnel and the precautions to be taken to ensure safety.

None

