#### H. Benefits:

1. The risks must be reasonable in relation to anticipated benefits, if any, to subjects, and to the importance of the knowledge reasonably expected to result.

2. The use of modest compensation for the burdens imposed by the research may be permitted, especially if benefits are minimal, but should be incremental and not conditioned on completion of the entire study.

3. Explain the expected benefits, if any, and their likelihood. If none, say so.

4. You may mention general benefits for science, or for other persons, if any.

These results will potentially help inform protocol for urologic procedures in the future. The use of B&O suppositories according to this protocol could help reduce the pain and discomfort of bladder and ureteral spasms that patients experience following lithotripsy procedures as well as decrease these patients' need for pain medication and thus reduce associated side effects of those medications in the post-operative period.

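### Side effects of a routine B and O dose are not collected uniformly across the arms, so a result favouring prophylaxis could not be set against a reliable harm comparison

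*Combined protocol and SAP*

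**What the plan says.** **Exposure.** Section D, step 2, sets up three arms. The Preoperative OR group is one "which will receive a B and O suppository after the induction of anesthesia prior to beginning the urologic procedure". The Postoperative OR group receives its suppository at the end of the procedure, before leaving the operating room. In both arms the dose is given to everyone, whether or not spasm develops.

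**Planned data.** Under section D, step 3, "all subjects will be given a quick survey within 24 hours to assess their amount of discomfort related to bladder spasms/urinary discomfort". The same step has charts reviewed for the amounts of antimuscarinic, narcotic and non-narcotic analgesic given. It mentions no side-effect item.

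**Other events.** Section D, step 5, leaves follow-up to the attending urologist and then says: "If, as part of that follow-up, clinically relevant events occur, the corresponding data will be recorded in the database". It gives no definition of relevance, event list, schedule or time window.

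**Safety provisions.** Question 2 of section G asks how data will be monitored for subjects' safety. The answer is that patients will be monitored after surgery and "any adverse effects will be treated as part of the normal post-operative course of care".

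**Expected harms.** The answer to question 5 of section G rates constipation and dry mouth as common (21-100 per 100) and blurred vision, dizziness, nausea, vomiting and light sensitivity as rare (under 5 per 100). Between them stands "Occasional: difficulty urinating" (5-20 per 100). All are placed within 1-2 days of treatment.

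**Analysis.** The analysis paragraph and sample-size answer in section D name no safety outcome.

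**The concern.** Treating spasm on demand exposes only patients who have symptoms. Prophylaxis also exposes those who would have had none, and for them the dose can bring side effects but no relief of spasm. The case for routine use therefore depends on harms as well as on pain and rescue medication.

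As written, whether a dry mouth or a hesitant void reaches the database depends on what follow-up a patient happens to have and on someone's view of its relevance. Section D offers different spasm treatments by arm after surgery, which implies that treating staff know the allocation. Under-recording can then be unequal between arms, and that biases the harm comparison as well as making it less precise. A favourable efficacy result could be used to support routine prophylaxis with no dependable harm figures beside it.

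**Working it through.** **1. Harms against collection.** For each effect the protocol names, is there a planned measurement?

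- Constipation, dry mouth, nausea, vomiting, dizziness, drowsiness: none described. They reach the database only through section D, step 5.
- Difficulty urinating or retention: the survey's urinary-discomfort item may overlap, but discomfort is not the same as difficulty voiding.
- Amounts of analgesic and antimuscarinic: yes, by chart review. These are efficacy measures.

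**2. The plan's own figure.** No safety figure is stated. The nearest is the binary rescue-medication outcome: 40% against 20%, two-sided alpha 0.05, 80% power. The pooled-variance formula gives

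n = [1.96 × √(2 × 0.30 × 0.70) + 0.8416 × √(0.40 × 0.60 + 0.20 × 0.80)]² / 0.20² = (1.270 + 0.532)² / 0.04 ≈ 81.2,

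so 82 per group, as stated. Nothing in that figure needs correcting.

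**3. Number exposed (assumption).** 180 / 3 = 60 per arm, so 2 × 60 = 120 receive a prophylactic dose. The sample-size answer speaks of equal randomisation across treatment and control groups. If that meant two halves, 90 would be exposed.

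**4. Exposed without need.** On the protocol's assumption that 40% of controls need spasm medication, (1 − 0.40) × 120 = 72 patients are dosed without needing it. With the 60% oxybutynin use that the protocol cites from one of the prostatectomy studies, the number is (1 − 0.60) × 120 = 48.

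**5. Expected cases among the exposed.** These use the form's category bands, which are not estimates.

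- Difficulty urinating: 0.05 × 120 = 6 to 0.20 × 120 = 24. With 90 exposed: 4.5 to 18.
- Each common effect: at least 0.21 × 120 ≈ 25.
- Each rare effect: fewer than 0.05 × 60 = 3 per arm, too few for a chi-squared test.

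**6. Precision with complete recording.** The half-width for a difference is 1.96 × √[p(1 − p)(1/n₁ + 1/n₂)].

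- 60 against 60: p = 0.05 gives 0.078; p = 0.20 gives 0.143.
- 120 against 60: p = 0.05 gives 0.068; p = 0.20 gives 0.124.
- If 90 are exposed, one active arm of 45 against 90 controls has 1/45 + 1/90 = 2/60, the same as 60 against 60.

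At low counts the normal approximation fails. The exact 95% interval for 3/60 is 1.0% to 13.9%. No events in 120 would give a one-sided 95% upper limit of 1 − 0.05^(1/120) ≈ 2.5%, but only if events had been looked for.

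**7. What incomplete recording does (illustrative assumptions).** Take true rates of 20% in 120 exposed and 5% in 60 controls. Power is about 80% with full capture, 42% if half of events are captured in every arm, and 19% if a quarter are. Unequal capture is worse. If the true rate were 20% in both groups, with full capture in one and half in the other, the data would show 20% against 0.5 × 20% = 10%, a false difference of 10 points.

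**The case against.** The strongest reply is that the plan does not ignore harms. Patients are monitored, clinically relevant events go into the database, higher-risk patients are excluded, and the drug is in established use for spasm. The survey form belongs to an appendix that is not reproduced, so a side-effect item cannot be ruled out. This stands as far as it goes: it would be wrong to say that no harm will be recorded. It does not supply a uniform method, and section D describes the survey as covering discomfort only.

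Three stronger readings are tempting, and the documents do not support them.

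- A reader might infer that section G understates exposure when it says of patients with spasms "but those that do will be exposed to possible side effects with treatment". That sentence closes a discussion of alternative treatments. The same answer opens with the risks of the suppositories without limiting them to patients with spasm, and section D is plain that both OR groups are dosed.
- A reader might take the hope in section H to "thus reduce associated side effects of those medications in the post-operative period" as a trial claim left untested. It is worded as a possibility, concerns the side effects of other pain medication, and is not part of the hypothesis in section A.
- A reader might say that the attending decides what is recorded. Step 5 puts follow-up with the attending but does not say who judges relevance or enters the data.

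There are also fair points about any remedy. Several side-effect tests would raise multiplicity, rare effects do not suit chi-squared, narcotics and Ditropan may be used in every arm, and a survey within 24 hours does not cover a 1-2 day risk period. These affect how the data should be collected and reported. They do not justify leaving collection to discretion.

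**Conclusion.** The point holds in a limited form. Side-effect ascertainment is neither uniform nor defined, so a harm comparison between the arms would be unreliable. It would not be absent, and the efficacy outcomes are untouched. This is a worthwhile and inexpensive improvement, not a flaw that invalidates the trial.

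The expected counts and the 8 to 14 point half-width rest on an equal three-way split, on category bands used as rates, and on similar rates in the two arms compared. The trial could therefore give rough estimates for the common and occasional effects. It could not settle the rare ones. The capture fractions in the working are assumptions chosen for illustration; the documents give no basis for a particular value.

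**What to change.** 1. Add to the existing 24-hour survey and chart abstraction a fixed yes/no list of effects that section G names: difficulty urinating or retention, nausea or vomiting, drowsiness, dizziness, dry mouth, constipation. Complete it identically in all three arms, whether or not an effect is judged relevant.
2. State the time window. If it stays at 24 hours, acknowledge that later effects, constipation in particular, may be missed. Covering the full 1-2 day period may need a later contact that the plan does not now include.
3. Report rates and between-arm differences by randomised arm, descriptively and with confidence intervals, using exact methods for effects rated rare. No significance tests are needed, so multiplicity does not arise.
4. Reconcile section D, step 2, under which controls may receive a suppository after surgery, with step 3, under which patients outside the experimental arm are not given one. Any between-arm harm contrast depends on which applies.

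The cost is a slightly longer form. With the window kept at 24 hours, no new visits are needed.
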